Subjects will receive 4 sterile cups and receive education on mid-stream urine collection. Day 1 will begin 5p.m. on the day before first morning void is collected. Subjects will collect 20-30 ml urine per collection. The cup will be marked at the 20-30 ml line to indicate how much urine should be collected. First morning voids: Subjects will be instructed to refrigerate their first voids. [10, 17] Time of void and time of presentation of specimen to study representative will be recorded to track how the length of that interval affects composition. The 2nd, 3rd and 4th void samples will be collected in the office during the designated times, and given to study personnel for dipstick analysis. Subsequently, the samples will be frozen, and batch sent to Litholink (Litholink, LabCorp Specialty Testing Group, Corporate Office [name]).

Table 1 – Study schematic

	Day 1	Day 2	Day 3	Day 4
	5 pm day before – 5pm	5 pm – 5pm	5 pm – 5pm	5 pm – 5pm
Fluid intake Record volumes and times of day True Lemon drink mix in one	Normal intake – record all	Normal intake – record all 5 pm – 12 am: Drink one bottle	Double daily intake - record all 5 pm – 12 am: Drink one bottle	Double daily intake - record all 5 pm – 12 am: Drink one bottle
bottle of Poland Spring water, 16.9 oz (500 mL)		Brillik One bottle	Dillik one bottle	Dillik one bottle
Urine void times - record times of all voids, and collect 20 – 30 mL samples at the specified times	First void, 9-10 am, 1-2 pm, 4-5 pm	-	-	First void, 9-10 am, 1-2 pm, 4-5 pm
Food intake – record times of all meals and snacks	Record all	-	-	Record all

1) Day 1: Normal Drinking Habits

- a. Day 1 begins at 5pm (the night prior to the 1st urine collection)
- b. All subjects will collect spot urine sample on the first void at home, then at 9-10AM, 1-2 PM and 4-5PM. They will be provided 4 sterile urine cups labeled for the different timed collections.
- c. Subjects will be educated on how to collect a mid-stream specimen. Females will further be instructed to void normally without cleansing as this adds an extra layer of burden on participants and studies have demonstrated that mid-stream non-cleansed sample is not inferior to a cleansed mid-stream specimen. [11, 16-19]
- d. Starting on Day 1 at 5pm until 5pm the following day subjects will be asked to record the times they eat, and to record their approximate fluid intake. Post-prandial urine excretion may be different compared to other voids. [20]

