- 4) UA dipsticks will be used in office to evaluate for pH and specific gravity dipsticks are within 0.5 pH effective accurate compared to pH meters.^[21] Dipstick analysis should be done as soon as possible after the urine is collected as pH changes the longer it is left out as a result of the natural breakdown of urea.^[12] It will be analyzed by study coordinators. Samples will also be sent to lab for evaluation of chemical composition of creatinine, citrate, and calcium. Electrolytes will be indexed against creatinine to evaluate their concentrations without having a 24-hour void volume amount.^[5, 9] A pH-meter will also be used to correlate the accuracy of pH values reported by the dipsticks.
- 5) All urines will be frozen immediately upon acquisition until batch sent to Litholink for electrolyte and pH analysis. [10, 17] All samples will only be identifiable by the study identification number. The lab will be instructed to discard all samples after the necessary tests are conducted.
- 6) A sample of citrate-Poland Spring will be sent to Litholink for analysis of Calcium and Citrate for reference.

C. SUBJECT POPULATION

- Healthy adult subjects will be accrued from outpatient urology office employees, residents, medical students, and faculty members who volunteer to participate in the study. A recruitment flyer will be posted in the outpatient Urology office and given to interested persons. A recruitment email will also be sent to office personnel, residents, medical students and faculty.

- The study will recruit 20-30 subjects.

D. DATA ANALYSIS

- Data collected with respect to subject demographics will include that from the questionnaire, including use of medications that affect kidney excretion, body weight and height, age, history of kidney disease or stones, types of diet, and supplements use. These points will be linked with the subject's urinalysis and urine chemistry results, however the subject's name will be removed during the statistical analysis. Data will be stratified by these demographics to identify any patterns that could potentially be studied by future studies.
- Those subjects who identify as having renal disease/history of nephrolithiasis, or who take diuretics will be excluded from the study. Those who are required to be on a fluid restriction for their health will not be allowed to participate in the study for safety reasons. Those that do not have voids at the appropriate time intervals will also be excluded.

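### A correlation with the pH meter cannot show whether the dipsticks are accurate; the pH source for the ANOVA is not named; and a first-void pH difference may include handling.

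*Combined protocol and SAP*

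**What the plan says.** **Measurement of pH (Section B, item 4).** "UA dipsticks will be used in office to evaluate for pH and specific gravity", and the text adds that "dipsticks are within 0.5 pH effective accurate compared to pH meters". The comparison between the two instruments is described in one sentence: "A pH-meter will also be used to correlate the accuracy of pH values reported by the dipsticks". Neither Section B nor Section D names a statistic for it. Item 4 lists creatinine, citrate and calcium for the laboratory; item 5 adds laboratory pH. Section D lists pH among the variables for the repeated measures ANOVA without saying which of the three readings is meant.

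**Handling of the samples (Section B, text before Table 1).** "First morning voids: Subjects will be instructed to refrigerate their first voids". The time of void and the time of hand-over "will be recorded to track how the length of that interval affects composition". By contrast, "The 2nd, 3rd and 4th void samples will be collected in the office during the designated times" and are passed to staff for dipstick testing. Item 4 warns that "pH changes the longer it is left out as a result of the natural breakdown of urea". Section A accepts analysis up to 4 hours after the void for refrigerated urine. It also names rough handling and loss of carbon dioxide as reasons for a more alkaline reading.

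**Analysis (Section D).** It plans stratification by questionnaire data, a repeated measures ANOVA, and a comparison of doubled with normal fluid intake. It does not mention the recorded interval or the dipstick-meter comparison.

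**The concern.** Two issues bear on how far a pH result can be trusted.

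First, accuracy is a question of agreement: how far the dipstick reading lies from the meter reading. Correlation asks only whether the two rise and fall together. A dipstick that read 0.5 pH too high on every sample would correlate with the meter as well as an unbiased one. If the check is carried out as worded, a high r could be reported as support for accuracy when the cited tolerance is not met. With three possible pH values and none designated, the choice could also be made after the results are seen.

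Second, void position and handling go together. The first void is the only one that waits in a refrigerator and travels. If any drift remains after refrigeration, it enters the first-versus-later contrast and looks like a time-of-day effect, or hides one. Variation in pH through the day is in the study title, so a reader will look at that contrast.

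**Working it through.** **1. The plan's own figures.** The figure that matters here is the 0.5 pH accuracy in item 4. It is a cited tolerance, so there is nothing to recompute. For completeness, the 87% power in Section D reproduces: two groups of 20, a difference of 1 SD and two-sided alpha 0.05 give 86.9% (noncentral t). It does not bear on this point.

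**2. Correlation against agreement.** The documents give no pH SD or dipstick error. Assume a meter SD of 0.6 and dipstick = meter + constant bias + scatter, with scatter SD 0.2.

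- Correlation: r = 0.6 / sqrt(0.6² + 0.2²) = 0.6 / sqrt(0.40) = 0.95. The bias does not appear in the formula.
- 95% limits of agreement: bias ± 1.96 × 0.2 = bias ± 0.39.
- Share within 0.5 pH: Φ((0.5 − bias)/0.2) − Φ((−0.5 − bias)/0.2).

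| Bias | r | Limits of agreement | Share within 0.5 pH |
|---|---|---|---|
| 0 | 0.95 | −0.39 to 0.39 | 98.8% |
| 0.5 | 0.95 | 0.11 to 0.89 | 50.0% |

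A simulation with the dipstick read to the nearest 0.5 and a meter SD of 0.7 shows the same pattern. For a bias of 0, 0.5 and 1.0, r stays at 0.94 while the share within 0.5 pH is 96%, 50% and 2%.

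Precision is adequate. The 95% confidence half-width of each limit is about 1.96 × 0.2 × sqrt(3/m). That is 0.05 if all 20 × 8 = 160 samples counted as independent, and 0.15 if only m = 20 did. Because each subject gives eight samples, the true value lies between the two.

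**3. What a handling drift could do.** Assume n = 20, pH SD 0.5 to 0.8, no true time-of-day effect, and a paired two-sided 5% test of the first void against one later void. The SD of the difference is SD × sqrt(2(1 − ρ)). Chance of a significant result (noncentral t, 19 df):

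| Assumed drift | ρ = 0 | ρ = 0.5 |
|---|---|---|
| 0.1 pH | 7–9% | 8–14% |
| 0.2 pH | 12–23% | 19–40% |
| 0.3 pH | 20–44% | 36–72% |

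The four-void ANOVA on one day (compound symmetry, 3 and 57 df) gives similar values, for example 11–21% and 17–40% at 0.2 pH. These rows show sensitivity to an assumed drift. They are not evidence that a drift exists.

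**4. Whether an analysis could remove it.** Office voids should have an interval near zero, so the interval as a covariate over all voids nearly duplicates void position. Two alternatives remain, and neither works well.

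- *Exclude first voids beyond 4 hours.* Assume linear drift and evenly spread delays. For delays of 1–5 hours the mean falls from 3.0 to 2.5 hours, leaving 2.5/3.0 = 83% of the mean drift. For 2–5 hours it falls from 3.5 to 3.0, leaving 86%. If only 20% exceed the limit, delays run over 1–4.75 or 2–4.5 hours, leaving 2.5/2.875 = 87% or 3.0/3.25 = 92%. Moreover, the 4 hours in Section A run to analysis, while Section B records time to presentation.
- *Slope of pH on interval among first voids.* With 20 subjects, the same interval on both days, interval SD 1 hour and ρ = 0.5 (all assumed), the 95% half-width is t(18) × SD × sqrt(0.75/19) = 0.21 to 0.33 pH per hour. A drift of 0.1 to 0.3 pH over a 3-hour mean delay is 0.03 to 0.10 per hour, for which power is about 5–16%.

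**The case against.** The defence has several good arguments.

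- *The word may be loose.* The sentence speaks of accuracy, and the team may intend a proper comparison. This stands as a caveat, but no agreement measure appears anywhere, so the plan does not secure one.
- *The check is ancillary.* The dipstick-meter comparison is not a Section D variable, and a constant dipstick bias cancels in within-subject contrasts. This stands and limits the severity.
- *The interval is not forgotten.* A reader might infer that the plan ignores handling. It does not: Section B records the interval and states why. Only a method in Section D is missing.
- *Handling is controlled.* First voids are refrigerated, which is the storage condition for the 4-hour allowance in Section A. The warning in item 4 concerns urine left out. If first voids are handed over at the 9–10 am visit (assumed), only those passed before 5–6 am exceed 4 hours. This stands; any remaining drift may be small.
- *The ANOVA is not at fault.* A reader might infer that a better model would separate handling from time of day. The overlap comes from home collection, and step 4 of the working shows that no analysis repairs it.
- *The freezing wording is editorial.* Item 5 can be read as contradicting home refrigeration and dipstick testing before freezing. However, the text before Table 1 says "Subsequently, the samples will be frozen, and batch sent to Litholink", after the dipstick step, and acquisition may mean receipt by staff. The passages should be reconciled, but they do not show a flaw in the analysis.

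**Conclusion.** The point holds and is minor. The firm part is that correlation cannot test the cited 0.5 pH accuracy; this is a mathematical property, and only the illustrative r of 0.95 and the shares within tolerance rest on assumed SDs. That the pH source for the ANOVA is unnamed can be read directly from items 4 and 5 and Section D.

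The handling part is a limitation of interpretation. The documents give no drift for refrigerated urine, no pH SD and no within-subject correlation, so its size is unknown. They do not support the inference that the pH results will be biased or that false positives will be frequent. Neither hypothesis in Section A names pH. The Day 1 versus Day 4 comparison is largely protected as long as first-void intervals are similar on the two days.

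**What to change.** 1. Replace the correlation in Section B, item 4, with the mean dipstick-minus-meter difference, its 95% limits of agreement (computed to allow for repeated samples per subject), and the share of readings within 0.5 pH.
2. In Section D, name one pH source for the repeated measures ANOVA before analysis. If the meter is read on every sample, use the meter value. Bring the laboratory analytes in items 4 and 5 into line at the same time.
3. Report the void-to-presentation intervals of first voids descriptively for Day 1 and Day 4, and state in the conclusion that a first-versus-later pH difference may include handling.
4. Treat an analysis excluding first voids beyond 4 hours, or a slope of pH on interval, as optional. Neither should be presented as a correction.

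The cost is a few lines of analysis and reporting on data already planned, with no new samples.

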Further, AUA guidelines for stone formers is to have a target urine volume output of 2.5L as the primary treatment option in those who are not fluid restricted secondary to renal or heart disease. [4] Multiple studies have demonstrated that increasing fluid intake leads to a reduction in kidney stones, as well as the general observation that non-stone formers have a larger mean urine volume compared to stone-formers. [2, 15] In the clinical setting, the clinician can assess hydration beyond measuring urine volumes is looking at specific gravity as a metric of assessing relative hydration. [12] However the hour to hour changes related to someone who increases their fluid intake have not been evaluated. Thus, we posit to assess how doubling oral fluid intake impacts chemical composition, pH and specific gravity over the course of a day. Similarly, increasing citrate consumption is also recommended but little is known about the hour to hour changes in the urine as a result.

Hypothesis:

- 1) 1st morning spot urine is more concentrated than others during the day, and the excretion of calcium and other electrolytes will significantly vary during the day.
- 2) Increasing fluid intake reduces urinary concentration but does not change calcium excretion.

B. STUDY DESIGN

Research team will consent subjects in the Urology Clinic office. Subjects will all get a questionnaire asking about weight, height, history of kidney stones, whether they are on any diuretics, medications that alter urine chemistries, or special diets.^[14] BMI will be calculated and stratified to assess whether the day-to-day variations are different for those with larger BMI. **Those taking diuretics, have known kidney disease or history of known nephrolithiasis will be excluded.** Those that do not comply with the void times on Day 1 and 2 will be excluded. ^[10]

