- e. Subjects will be asked not to void outside of the timed collections. If they do void outside of these times, they will be asked to record the extra times that they void.

2) Day 2 and 3: True lemon Intake

a. Day 2 will begin 5p.m after the last collected void of Day 1.

b. Subjects will be provided 3 True Lemon packets (True Citrus, [name]). They will be instructed to mix 1 packet in one 16.9oz (500 mL) bottle of Poland Spring water (Nestle Waters North America). They will drink one bottle on Day 2 after 5 p.m., and another bottle after 5pm on Day 3, All True Lemon packets and Poland Spring bottles will be provided to subjects by the research study team.

- c. Subjects will be asked to record the time and the approximate volume of their fluid intake. Subjects will record the 2 True Lemon water bottle intakes, as well as any additional fluid intake they have.
- d. On Day 3 all subjects will be asked to double their fluid intake based on the previous days' diaries.

3) Day 4

- a. Day 4 will begin at 5pm (the night prior to urine collection) and the subjects will drink the last bottle of water with True lemon.
- b. All subjects will collect spot urine sample on the first void at home, then at 9-10AM, 1-2 PM and 4-5PM.
- c. Subjects will be asked to record the times they eat, and to record their approximate fluid intake and times of intake. Subjects will also be asked to double their fluid intake, using Day 1 and Day 2 as a guide of their normal daily intake (including the True Lemon Bottle volume).
- d. Subjects will be asked not to void outside of the timed collections. If they do void outside of these times, they will be asked to record the times of the extra voids.
- e. Subjects will be educated on how to collect a mid-stream specimen. Females will further be instructed to void normally without cleansing as this adds an extra layer of burden on participants and studies have demonstrated that mid-stream non-cleansed sample is not inferior to a cleansed mid-stream specimen.^[11, 16-19]

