- Data analysis will be conducted by [name] and [name] at Albany Medical Center.
- All questionnaires and diaries will be kept in research office, input into password-protected software, and analyzed at Albany Medical Center.
- Data Points: After discussing data points with [name] the study will aim to recruit at least twenty subjects, which will give 87% power to detect a difference in any urine variable that is at least as large as one standard deviation of that variable in the normal fluid intake session (two tailed alpha of 0.05). Since, assuming a normal distribution, one standard will encompass 68% of patients, we consider a one standard deviation difference to be the minimally important clinically significant difference in these measures. Data points will be statistically analyzed by a repeated measures ANOVA test. Further, changes in the below variables after doubling fluid intake will be calculated for statistically significant changes compared to normal fluid intake.
 - o pH
 - o Specific gravity,
 - o Calcium
 - o Creatinine
 - Citrate
 - o Changes in the above after doubling fluid intake

E. RISKS

- There are minimal risks to this study.
- If subjects are on a fluid restricted diet, the second component of the study could potentially be harmful to their health. For this reason, these subjects will be excluded from the study
- There is a risk that there is a violation of privacy due to a breach in study data. However, the data will not be able to be linked to a specific individual.
- There is a risk of exposing underlying illness while evaluating urines of otherwise healthy subjects.

F. BENEFITS

- The main benefits of this study are to improve the quality of care provided to stone-forming patients in the urologic clinical setting.

- Add to the general medical knowledge about urine composition and its variation.

G. CONFIDENTIALITY

- After consent is collected, all subjects will receive and be referred to by a study number ie. 1, 2, etc., which all collected specimens and documentations will utilize. The master key containing the names and corresponding study numbers will be securely stored on an AMC network drive to which only the research staff have access. The master key will be destroyed after all data collection and analysis.
- A portion of the subjects' past medical history and current medication regimens will be collected, but their name will be replaced by a study ID# to de-identify the data please see questionnaire.

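### Day 4 minus Day 1 measures doubled fluid, True Lemon and day order together, but the aim and Hypothesis 2 state it as a fluid effect and Section D labels it as one

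*Combined protocol and SAP*

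**What the plan says.** Section A gives the second aim as "we posit to assess how doubling oral fluid intake impacts chemical composition, pH and specific gravity over the course of a day". Hypothesis 2 reads "Increasing fluid intake reduces urinary concentration but does not change calcium excretion". Section A also mentions citrate consumption as an interest, but no citrate hypothesis or contrast follows from it.

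In Section B, Table 1 sets urine collection at "First void, 9-10 am, 1-2 pm, 4-5 pm" on Day 1 and Day 4; the cells for Days 2 and 3 hold a dash. Day 1 is normal intake without True Lemon. The True Lemon row, "5 pm – 12 am: Drink one bottle", applies to Days 2, 3 and 4. Fluid is doubled on Days 3 and 4. Item 3a says that on Day 4 "the subjects will drink the last bottle of water with True lemon". The four days run consecutively and in the same order for everyone. Item 6 adds: "A sample of citrate-Poland Spring will be sent to Litholink for analysis of Calcium and Citrate for reference".

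Section D (Data Points) plans a repeated measures ANOVA and says that "changes in the below variables after doubling fluid intake will be calculated for statistically significant changes compared to normal fluid intake". The variables are pH, specific gravity, calcium, creatinine and citrate. True Lemon is not named there, and no adjustment for it is planned.

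**The concern.** No sampled day has doubled fluid without True Lemon, or True Lemon with normal fluid, and no subject takes the days in another order. A change between the two sampled days could come from any of the three, yet the stated aim and hypothesis credit it to fluid.

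The error could run in two directions. A change in citrate or calcium/creatinine could be reported as a fluid effect although the drink caused some or all of it. Conversely, a drink effect that partly offsets a fluid effect would make a null result more likely, and Hypothesis 2 predicts no change in calcium excretion. The interest in hour-to-hour changes from citrate cannot be answered separately either.

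**Working it through.** **1. What the sampled days can estimate.** Inputs: Table 1 and items 1 to 3 of Section B. Code each sampled day as (intercept, doubled fluid, True Lemon, later day):

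- Day 1 = (1, 0, 0, 0)
- Day 4 = (1, 1, 1, 1)

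Two rows give rank 2 for four parameters. Without the day term the rank is still 2, for three parameters. The difference is fluid + True Lemon + day order, and no sample size splits it. This result needs no assumed effect size.

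**2. The plan's own power figure.** Section D claims "87% power to detect a difference in any urine variable that is at least as large as one standard deviation of that variable", with 20 subjects and two-sided alpha 0.05. A two-sample t calculation with n=20 per session and d=1 has 2n-2 = 38 degrees of freedom and noncentrality d√(n/2) = √10 = 3.16. Power is 0.869, which reproduces the 87%.

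**3. Illustration: the fluid effect is zero and the drink shifts the variable by 0.5 SD (assumed).**

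- Two-sample, n=20: noncentrality 0.5 × √10 = 1.58; probability of significance 0.338.
- Paired, n=20: standardised difference d/√(2(1-r)), multiplied by √20. The correlation r is assumed, since the documents give none.
  - r=0: 0.5/√2 = 0.354, noncentrality 1.58, probability 0.324.
  - r=0.5: 0.5/√1 = 0.5, noncentrality 2.24, probability 0.565.
  - r=0.7: 0.5/√0.6 = 0.645, noncentrality 2.89, probability 0.782.
- At n=30, the upper end of planned recruitment, the two-sample figure rises to 0.478. More subjects make a wrong attribution more likely.

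**4. Illustration: the true fluid effect is 1 SD and the drink works against it (assumed), n=20.**

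| Drink offset | Net shift | Two-sample | Paired, r=0.5 |
|---|---|---|---|
| none | 1 SD | 0.869 | 0.989 |
| 0.25 SD | 0.75 SD | 0.637 | 0.889 |
| 0.5 SD | 0.5 SD | 0.338 | 0.565 |

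Pairing softens the loss for small offsets. The same pairing raises the risk in step 3.

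**5. Time from bottle to void.** The shortest interval is the earliest void time minus midnight; the longest is the latest void time minus 5 pm the evening before.

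- 9-10 am void: 9 to 17 h
- 1-2 pm void: 13 to 21 h
- 4-5 pm void: 16 to 24 h

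The first void comes soonest after the bottle, at no fixed clock time. A drink effect may therefore differ between voids, so the single-shift figures above are not specific to any void.

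**The case against.** The strongest reply is that nothing in the documents shows that True Lemon changes the urine by any given amount. That stands. The probabilities in steps 3 and 4 are ordinary power curves applied to assumed shifts, and the 9 to 24 h gap before the three timed voids may weaken any effect. They show what a shift would do, not that one exists.

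Section D's phrase may also be only a label for the session, matching its earlier reference to the normal-intake session. That is a fair reading of Section D taken alone. It does not help the aim or Hypothesis 2, which are worded as effects of fluid.

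The plan has several features that might seem to answer the point. Assaying the drink and keeping diaries measure exposure. Counting the bottle in the reference intake deals with volume, not with citrate or calcium content. Creatinine indexing corrects for dilution. None supplies the missing comparison, because every subject changes fluid, drink and day together.

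A reader might go further and infer that the drink undermines the concentration half of Hypothesis 2, or that the study as a whole is compromised. The documents do not support either inference. No drink effect on specific gravity or creatinine is shown; for those the caveat is day order, which applies to any before-and-after design and for which no specific drift is identified. Hypothesis 1 can be tested within Day 1, before any True Lemon or doubling.

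**Conclusion.** The point holds. Day 4 minus Day 1 estimates a joint effect, and the aim and Hypothesis 2 claim more than that. This follows from the sampling schedule alone and cannot be repaired by analysis of the urine collected.

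Its reach differs by variable. It is most direct for citrate, which the drink supplies. It bears on calcium/creatinine, where Hypothesis 2 predicts no change. It is possible for pH. Specific gravity and creatinine carry only the day-order caveat.

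The documents give no size, direction or duration for a drink effect, so the bias is not quantified. A reader might take 34%, or 32-78%, as the study's false-positive rate. It is not: those figures require an assumed 0.5 SD drink shift, zero fluid effect, n=20 and, for the paired range, an assumed correlation of 0 to 0.7. On the same footing, a 0.5 SD offset to a 1 SD fluid effect would cut detection from 87% to 34% (two-sample), or from 99% to 57% (paired, correlation 0.5).

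**What to change.** Change the wording in three places, and make the title's reference to increased fluid intake consistent with them. Suggested text:

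- **Aim (Section A):** *to describe how urine chemistry, pH and specific gravity differ across the day when doubled fluid intake and True Lemon are taken together (Day 4 versus Day 1, fixed order).*
- **Hypothesis 2:** *Doubled fluid intake together with True Lemon lowers urinary concentration and leaves calcium excretion unchanged (Day 4 versus Day 1, fixed day order).*
- **Section D:** *Day 4 minus Day 1 estimates the joint effect of doubled fluid intake and True Lemon in a fixed day order. Changes in citrate, calcium/creatinine or pH will not be attributed to fluid alone. Absence of change in calcium/creatinine will not be read as showing that fluid has no effect. No separate citrate effect will be claimed. Day order is a limitation for every variable, including specific gravity and creatinine.*

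This needs no added samples, visits or subjects, and leaves the intake schedule as it is. The cost is narrower conclusions: the study could no longer claim a fluid-only effect on calcium excretion, citrate or pH.

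### A missed timed void removes the whole subject after enrolment, which discards valid samples, selects the analysed set on compliance, and is not allowed for in the sample size

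*Combined protocol and SAP*

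**What the plan says.** The exclusion appears twice. Section D (Data Analysis), in the same item as renal disease, stone history, diuretic use and fluid restriction, adds: "Those that do not have voids at the appropriate time intervals will also be excluded". It names no day. Section B (Study Design) has: "Those that do not comply with the void times on Day 1 and 2 will be excluded". Table 1 schedules urine samples on Day 1 and Day 4 only.

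On each collection day the schedule is: "All subjects will collect spot urine sample on the first void at home, then at 9-10AM, 1-2 PM and 4-5PM". That makes four samples a day and eight per subject, six of them in one-hour windows.

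On Day 4, "Subjects will also be asked to double their fluid intake". On both collection days, "Subjects will be asked not to void outside of the timed collections". Voids between windows are logged; for Day 4 the text is "If they do void outside of these times, they will be asked to record the times of the extra voids". Such voids are not named as a ground for exclusion.

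On numbers, Section C gives a recruitment range of 20 to 30. Section D says "the study will aim to recruit at least twenty subjects" and attaches 87% power to that number, for a difference of one standard deviation at two-sided alpha 0.05. The analysis is a repeated measures ANOVA. The documents state no rule for partial data, no missing-data method, no replacement of excluded subjects and no allowance for exclusions.

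**The concern.** The other exclusions listed beside this one can be checked at entry. This one can be judged only from what the subject does during the study and, under Section D's wording, partly after the intervention has started. Anyone who fails it loses all their data, including samples correctly given on both days.

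Two things are at stake. The first is selection. The ANOVA would be run on people who met every required window. If their daily pattern, or their response to doubled fluid, differs from that of the people removed, both the time-of-day profile and the fluid effect may be biased. Recruiting more subjects does not cure this. The second is precision: valid samples are thrown away, and the power statement counts people recruited rather than people analysed.

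The rule also sits poorly with the study's aim of supporting spot urines at clinic visits, which occur at varying times. A sample given shortly after a window closes still informs that aim, and its time is recorded.

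**Working it through.** **Inputs from the documents.** At least 20 subjects, range 20 to 30; difference 1 SD; two-sided alpha 0.05; stated power 87%; three one-hour windows on each of Days 1 and 4.

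**Assumptions, because the documents give no figure.** Miss rate per window p = 2%, 5% or 10%, with independent misses; within-subject correlation rho = 0.5 for the paired calculation.

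**1. Reproduce the 87%.** Two-sample t-test, n = 20 per session treated as independent: noncentrality = 1 × √(20/2) = 3.16 on 38 degrees of freedom, power 0.869. This matches. A paired t-test with n = 20 has noncentrality √20 / √(2(1 − rho)). It gives 0.851 at rho = 0, 0.868 at rho = 0.05, 0.933 at rho = 0.25 and 0.989 at rho = 0.5. The stated figure therefore corresponds to 20 evaluable subjects, no loss, and essentially no credit for pairing.

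**2. Power if exclusions reduce the analysed number.**

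| Analysed | Independent-samples basis | Paired, rho = 0.5 (assumed) |
|---|---|---|
| 20 | 0.869 | 0.989 |
| 18 | 0.830 | 0.979 |
| 15 | 0.753 | 0.949 |
| 13 | 0.687 | 0.911 |

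**3. Samples lost per exclusion.** Eight samples per subject; missing one and excluding the person discards 8 − 1 = 7 valid samples.

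**4. How many might remain.** Fraction complete over six windows = (1 − p)^6.

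| p | Fraction complete | Of 20 | Of 30 |
|---|---|---|---|
| 2% | 0.886 | 17.7 | 26.6 |
| 5% | 0.735 | 14.7 | 22.1 |
| 10% | 0.531 | 10.6 | 15.9 |

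If only the Day 1 windows count, which is one possible reading of Section B, the exponent is 3. At p = 5%, 0.95^3 = 0.857, leaving 17.1 of 20 or 25.7 of 30. Misses that cluster within a person would leave more complete subjects than either calculation shows.

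**5. Recruitment needed for 20 evaluable.** 20/(1 − d), rounded up, for an assumed exclusion fraction d: 22 at 5%, 23 at 10%, 25 at 20%, 30 at one third.

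**The case against.** The strongest reply is that the practical damage may be small. Twenty is a minimum: recruiting 30 could absorb ten exclusions, and at p = 2% or 5% more than twenty would be expected to remain. Each subject is their own control, so losing a person removes both days, and bias in the fluid effect arises only if the within-person change differs between those kept and those lost. Subjects are office staff, residents, students and faculty giving the timed samples in the office, so high miss rates need not be expected. All of this stands, and it makes power the secondary matter.

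A reader might go further and infer that the rule selects on urine flow in a known direction: low drinkers with nothing to give on Day 1, and high-flow subjects unable to hold on Day 4. The documents do not support that.

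- The shortest gap between windows is two hours (2 pm to 4 pm). Producing 30 mL in that time needs 15 mL/h, or 360 mL/day, against the 2.5 L/day target cited in Section A (about 104 mL/h).
- Extra voids are only recorded, so someone who also voids between windows still complies, and higher flow may make a sample easier to give.
- Misses may equally come from work schedules.
- Section A does say that "non-stone formers have a larger mean urine volume compared to stone-formers", but people with known stones are excluded, so it does not show that those lost would resemble stone formers.

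It is also fair that a mixed model assumes data missing at random and does not remove selection on unmeasured flow.

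None of this removes the core: the rule is subject-level, acts after enrolment, discards valid data, and has no counterpart in the sample size.

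**Conclusion.** The point holds in a limited form. The plan excludes whole subjects on behaviour observed during the study and makes no provision for partial data. One missed window can cost seven valid samples, and the repeated measures ANOVA would rest on a compliance-selected set. This may bias the time-of-day profile and the fluid effect; neither direction nor size can be derived.

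The 87% holds for 20 evaluable subjects on an independent-samples basis. If only 20 are recruited, each exclusion erodes it (0.830 at 18, 0.753 at 15). A reader might infer that the analysed number must fall below twenty. It does so only if recruitment stops near twenty and someone is excluded, or if exclusions exceed the margin recruited. With an assumed correlation of 0.5, power stays above 0.90 down to 13.

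Whether the rule reaches Day 4 depends on wording that must be reconciled: Section D is unrestricted, while Section B names Days 1 and 2, although no samples are scheduled on Day 2. Exclusion is of the whole subject under either wording. The retention figures rest on assumed, independent miss rates. This should be changed because the remedy is cheap, not because a large bias has been shown.

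**What to change.** - Replace the subject-level exclusion in Sections B and D with a sample-level rule: keep every enrolled eligible subject and set to missing only a sample not provided. State consistently which collection days and windows are meant.
- Analyse a sample given outside its window at its recorded time, provided it falls within the same study day (before 5 pm). A Day 1 sample after 5 pm belongs to Day 2, when the True Lemon bottle begins, and should count as missing for Day 1.
- Make a mixed model for repeated measures the main analysis, since it accepts incomplete profiles. Give the fully compliant subset as a sensitivity analysis.
- Report missed windows by day and reason, so that the plausibility of missing at random can be judged.
- State the power figure per evaluable subject, with an assumed loss and the recruitment it implies within the 20 to 30 range.

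The cost is one sentence in each of Sections B and D, a revised analysis statement and a revised sample-size sentence. No new visits, samples or assays are needed, because void times are already recorded. The downside is slightly more spread in collection times and reliance on missing at random. Extra voids between windows have a time but no scheduled sample, so they add no chemistry data.
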